7.8 Data Archiving

Once all primary and secondary analysis has been completed the trial data will be archived. Once the trial data has been archived the trial database will be decommissioned and will no longer be available. Any subsequent/ further analysis will be performed using the archived data.

7.9 Quality Issues

Quality Issues are issues that can have an impact on participant safety, rights, and well-being; data integrity and/or scientific rigor; and compliance with regulatory requirements; these can be classified as protocol deviations, potential serious breaches, near misses etc.

A protocol deviation is any departure from procedures documented in this protocol, this includes deviations that cannot be predicted. If a protocol deviation is identified the HWFinEL trial team should be contacted and CCTU's protocol deviation reporting process will be followed.

A 'serious breach' is a deviation from procedures documented in this protocol, GCP or other clinical trial regulations that is likely to affect to a significant degree:

1. The safety or physical or mental integrity of the participants in the trial, or
2. The scientific value of the trial.

If a serious breach is suspected the Sponsor must be contacted within 1 working day. In collaboration with the CI, the serious breach will be reviewed by the Sponsor and, if appropriate, the Sponsor will report it to the REC committee within 7 days.

8 Statistical Considerations

8.1 Sample Size

We make the following assumptions:

- I. We take the Minimum Clinically Important Difference (MCID) in PHQ-8¹¹ scores to be half of the usual value of 3. We have chosen this conservative estimate because the population at risk in this study is not known to have a high prevalence of depressive illness (unlike the other environments in which the PHQ-8 has been validated). Additionally, we are not convinced that this population, which encompasses a high proportion of migrants and people of minority ethnicity, will volunteer symptoms of a depressive disorder because of cultural stigma against mental illness. Further, those participants who experience symptoms of low mood may report different symptoms from those elicited on the PHQ scale due to cultural differences in the way they experience low mood. We therefore do not think the PHQ is an appropriately sensitive instrument in this environment and have estimated the sample size with a conservative estimate of the MCID.
- II. We have provided a conservative estimate of the correlation between baseline and follow-up values. This means that the study may be overpowered.
- III. We assume a standard deviation of 7.25 for the change score (which derives from the Born in Bradford study)¹⁶.
- IV. This is a very experienced research team which has conducted substantial research in this area. We have consulted extensively with our PPIE partners, and they do not think that we will encounter high dropout rates. We anticipate that we will have an approximate dropout rate of 10% but are prepared for a 20% dropout rate in our sample size calculations.
- V. We have used the ANCOVA method to calculate the sample size. This method results in a smaller sample size (if we account for baseline adjustment for PHQ-8 scores in the final analysis of the effect of the intervention) than that which would obtain otherwise.

We estimate that we will be able to detect a difference of 1.5 units in the PHQ-8 scale between the two arms with a two-sided alpha of 5% and with 90% power (assuming a nominal correlation of 0.25 between baseline and follow-up scores, a standard deviation of the change score of 7.25 and an anticipated 20% drop-out rate) with a sample size of 1153 participants.

If the dropout rate is only 10% (as anticipated), leaving all the other parameters as specified above, we expect that the study will have an increased power of 93% to find a difference in PHQ-8 scores of a magnitude of at least 1.5 units between the arms if such a difference exists.

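### Section 8.1 labels 7.25 as the SD of the change score, but 1153 participants, 90% and 93% power reproduce only if 7.25 is the SD of the PHQ-8 score itself

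*Protocol*

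**What the plan says.** Section 8.1 lists five numbered assumptions and then the result. Assumption III reads "We assume a standard deviation of 7.25 for the change score" and attributes the value to a Bradford cohort study. Assumption V reads "We have used the ANCOVA method to calculate the sample size". Assumption II reads "We have provided a conservative estimate of the correlation between baseline and follow-up values" and concludes that the study may be overpowered.

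The result sentence aims to "detect a difference of 1.5 units in the PHQ-8 scale between the two arms" with a "two-sided alpha of 5% and with 90% power". It assumes a correlation of 0.25 and "a standard deviation of the change score of 7.25 and an anticipated 20% drop-out rate) with a sample size of 1153 participants". The change-score label thus appears twice. For 10% dropout with everything else unchanged, the section adds: "we expect that the study will have an increased power of 93" per cent. No SD for the PHQ-8 score itself is given.

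The total of 1153 is carried into the summary table and Sections 3.3.1 and 3.3.5. In Section 3.3.4 (Table 1) the green recruitment threshold of 230 is described as about one fifth of the target.

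**The concern.** ANCOVA reduces the variance of the follow-up score by the factor 1 − r². That factor belongs with the SD of the score. A change score has already had the baseline subtracted, so its SD must first be converted to a score SD. Section 8.1 gives a change-score SD, names ANCOVA, and reports a total that appears to skip the conversion.

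At stake is whether the stated power is the power of this design under its own inputs. The direction of the correlation argument depends on the same point: a low r is cautious when the score SD is held fixed, and the opposite when the change SD is held fixed.

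**Working it through.** **Inputs (Section 8.1; 1:1 allocation from Section 8.2.2).** Difference 1.5; two-sided 5%, 90% power, so z = 1.960 + 1.2816 = 3.2416 and z² = 10.508; SD 7.25 (variance 52.56); r = 0.25, so 1 − r² = 0.9375; dropout 20% or 10%.

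Per arm, n = 2 × z² × residual variance / 1.5². Round up, double, then divide by 0.8.

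**1. Reproducing the published figures, with 7.25 as the score SD**
- Residual variance = 52.56 × 0.9375 = 49.28 (residual SD 7.02).
- n = 2 × 10.508 × 49.28 / 2.25 = 460.3, so 461 per arm and 922 in total; 922 / 0.8 = 1152.5, so **1153**.
- Power of 1153 is 90.1% at 20% dropout (922 analysed) and 93.1% at 10% (1038 analysed). A t-based calculation gives 90.0% and 93.0%.

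All three published figures match.

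**2. With 7.25 as the change SD, analysed as a plain change score**
- n = 2 × 10.508 × 52.56 / 2.25 = 491 per arm; 982 / 0.8 = 1227.5, so 1228.
- Power of 1153 is 88.1% and 91.5%.

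No match.

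**3. With 7.25 as the change SD, analysed by ANCOVA (as labelled)**

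This needs the relation between the two SDs. Assume that they are equal at baseline and follow-up.
- Change variance = 2 × score variance × (1 − r), so score variance = 52.56 / 1.5 = 35.04 (SD 5.92).
- Residual variance = 35.04 × 0.9375 = 32.85 (SD 5.73).
- n = 2 × 10.508 × 32.85 / 2.25 = 306.8, so 307 per arm; 614 / 0.8 = 767.5, so **768** (t-based 770).
- Power of 1153 is 97.8% at 20% dropout and 98.8% at 10%.
- Difference detectable with 90% power at 20% dropout = 3.2416 × 5.73 × √(2 / 461.2) = **1.22**.

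No match.

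**4. How far step 3 depends on equal SDs**

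Let k be the baseline SD divided by the follow-up SD. Then follow-up variance = 52.56 / (1 + k² − 2rk).

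| k | Follow-up variance | Residual variance | Total N at 20% dropout |
|---|---|---|---|
| 0.5 | 52.56 | 49.28 | 1153 |
| 0.8 | 42.39 | 39.74 | 930 |
| 1.0 | 35.04 | 32.85 | 768 |
| 1.25 | 27.13 | 25.43 | 595 |

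A true change SD of 7.25 would give 1153 if the baseline SD were half the follow-up SD (3.6 against 7.25). The protocol says nothing of the kind.

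**5. Direction of the correlation assumption**

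With the change SD fixed and equal SDs, residual variance = SD_change² × (1 + r) / 2, which rises with r. With the score SD fixed, it is SD² × (1 − r²), which falls with r.

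| r | N, 7.25 = change SD | N, 7.25 = score SD |
|---|---|---|
| 0.25 | 768 | 1153 |
| 0.4 | 860 | 1033 |
| 0.5 | 923 | 923 |
| 0.7 | 1045 | 628 |

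Assumption II is therefore true only in the right-hand column.

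**The case against.** The strongest reply is that this is a slip in a label. All three published figures fit the score-SD reading, and so does assumption II. On that view nothing needs recalculating and one word is surplus, twice. That may well be so, and the internal evidence leans that way. It does not remove the point: the label is given twice and tied to a cited source, and the protocol contains nothing that settles what the source reports.

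A second reply is that 768 is not fixed by the protocol's inputs, because it needs equal SDs at both times. This stands. The figure must carry that assumption and the range in step 4.

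A third is that the protocol already warns of overpowering. It does, but it attributes this to the low correlation. Under the change-SD reading a low correlation makes N smaller, so that explanation would not hold.

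A reader might go further and infer that 1153 and the stated powers are simply wrong, or that the trial is about 50% too large. The document does not support this: if 7.25 is the score SD, all of those figures are right. A reader might also infer that the required N governs the pilot's closure decision. Only the green threshold of 230 is described by reference to the target. The red trigger of fewer than 150 is a fixed count not linked to N, and the retention criteria are percentages.

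**Conclusion.** The concern holds as an inconsistency: the stated SD label and the stated calculation do not agree. That 1153, 90% and 93% come from using 7.25 as the score SD in the ANCOVA formula is firmly established by exact reproduction of all three. Which side is in error cannot be decided from the protocol.

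If the label is right, 90% power needs about 768 participants under equal SDs (930 to 595 for baseline to follow-up SD ratios of 0.8 to 1.25). The planned 1153 then gives about 97.8% and 98.8% power, or 90% power for about 1.22 points. If the label is wrong, the published figures stand unchanged. With equal SDs, neither reading leaves the trial below its stated power for 1.5 points under the ANCOVA method that it names.

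**What to change.** Check in the cited source whether 7.25 is the SD of the PHQ-8 score or of its change, then do one of the following.

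- **Score SD:** delete *change* in assumption III and in the result sentence. The figures 1153, 90% and 93% and assumption II remain as they are.
- **Change SD:** keep 1153, but restate its power (about 97.8% at 20% dropout and 98.8% at 10%) or its detectable difference (about 1.22 at 90% power and 20% dropout). State the equal-SD assumption, and correct assumption II, since a low correlation is then not the cautious choice. Recheck the description of the green threshold only if the target itself is changed.

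The cost is a look at one source and an amendment to the wording of Section 8.1. Enrolment and the analysis need not change.

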8.2 Assignment of Intervention

8.2.1 Randomisation Procedures

An independent, concealed, online randomisation service provider (www.sealedenvelope.com) will be used to divide participants equally into the two trial groups.

We will perform individual participant randomisation using stratification factors, detailed in the prespecified SAP, to attempt to balance allocation to both study arms for these variables. We will use a biased coin technique to ensure that the groups are approximately equal but still retaining some component of randomness in the allocation. Randomisation will be performed either by CCTU/UCL Researchers or by a delegated entity via Sealed Envelope (who will use industry standard validated randomisation and/or minimisation algorithms to achieve the aim of 1:1 allocation ratio with the 70% biased coin element of randomness). The Trial Statisticians conducting the trial analyses and involved in the conduct of the study will be blinded to trial group allocation until the end of the trial when data analysis and unblinding occurs.

Following the Baseline visit, the UCL Researcher or delegate will enter minimisation factors as well as the necessary data to re-confirm participant eligibility on the SealedEnvelope.com secure online system and then allocate the appropriate PIN to the participant.

Delegated staff (at CCTU/UCL Researchers or appropriate designee) will be provided with a secure login to the SealedEnvelope.com Website, according to their role in the trial. The randomisation result will be shown directly online as the intervention allocation, with an email confirmation sent to the user and to the CCTU trial team. If allocated to the intervention group, the UCL Researcher will book a WBA appointment and provide details to the participant.

Randomisation will be considered completed after allocation has been generated from the randomisation system.

8.2.2 Randomisation Method

Participants will be randomised 1:1 to the intervention group (WBA appointment) or the control group (standard of care, where they will be given information on where to access welfare benefits advice).

8.2.3 Sequence generation

Randomisation will be performed with stratification factors to attempt to achieve equal allocation to both study arms.

8.2.4 Allocation concealment mechanism

Treatment allocation will be masked to the trial statisticians during the conduct of the study by Sealed Envelope who will restrict access to the variable which encodes for allocation.

8.2.5 Allocation Implementation

After the participant's eligibility for the trial has been confirmed, they have provided informed consent, and baseline measures have been recorded, randomisation will be performed by

the CCTU or a delegated entity, using the Sealed Envelope randomisation service stated above. Eligibility and consent will be verified before each participant is randomised. Eligibility decisions will be made in line with the approved protocol.

8.2.6 Blinding

This is a randomised controlled trial with appropriately blinded statisticians and health economists during the conduct of the study. All analyses will be conducted by suitably qualified and experienced statisticians according to a detailed prespecified SAP. Investigators, participants, health visitors at the CFCs, and the WBAs will be unblinded. Process evaluation researchers, who will support participant recruitment and conduct the qualitative interviews, will not be blinded to group allocation.

Allocation concealment will be maintained by providing alternative Welfare Benefits advice to those who have been allocated to the control group. Participants who are randomised to the control group will be emailed or mailed a card detailing LBTH's existing 'service as usual' WBA services which reproduces what is available on their website (signposting to LBTH and voluntary sector welfare benefits advice service, national websites and helplines) after their follow up data is obtained and when sending on their thank you voucher.

The blinded intervention allocation identity will be maintained in the online Sealed Envelope randomisation service and the trial statistician will not have access to the variable which codes for intervention allocation.

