1.1.1 Explanation for choice of comparators/Intervention

We are comparing one group of participants who will receive welfare benefits advice from a welfare benefits advisor (WBA) that is co-located with routine 6-8 week newborn health appointments in a Children and Families Centre. The second group will receive standard care and be given information on where they can access welfare benefits advice.

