1.3 Trial Design

HWFinEL is a randomised controlled trial with appropriately blinded statisticians and health economists during the conduct of the study. All analyses will be conducted by suitably qualified and experienced statisticians according to a detailed prespecified statistical analysis plan (SAP).

Participants will be randomised, after completion of their baseline questionnaire, in a 1:1 ratio to the intervention group (WBA appointment) or the control group and will be unblinded to their group allocation. Additionally, WBAs and HVs involved in service delivery, and researchers conducting the process evaluation, will be unblinded to the group allocation.

Participants who are randomised to the intervention group will be contacted by telephone (by a UCL Researcher) and invited to attend a WBA appointment within 3 months of randomisation. Wherever possible, this will be timed to coincide with their baby's/babies' 6-8 week check.

Participants who are randomised to the control group will be emailed or posted a card to their address detailing LBTH's existing 'service as usual' WBA services which reproduces what is available on their website (signposting to LBTH and voluntary sector welfare benefits advice service, national websites and helplines).

All participants will be required to complete a baseline questionnaire and a 6-month follow-up questionnaire upon study completion. Participants will be reminded twice (by email, post or telephone – telephone being the first point of contact) to complete their questionnaires: for

two months after receiving the questionnaires, if these have not been completed. Therefore, the total duration of the trial for each participant will be up to 9 months.

Additionally, a subsample of 45 participants from both groups will be purposively selected at random to complete an in-depth interview after the 6-month follow-up (refer to section 10 for more information about the interviews which forms the process evaluation).

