3.3.3 Methods to increase response

The following strategies will be implemented to increase response rate and mitigate loss to follow-up in this trial:

1. Clear Informed Consent Process

We ensure that participants and their families fully understand the study's commitment and benefits through a transparent informed consent process. Families are only randomised after completing baseline questionnaires, which allows us to assess their initial commitment to participation.

2. Follow-up Reminders and Support

Reminders will be sent to participants to complete follow-up questionnaires and follow-up phone calls will be made to ensure participants remain engaged and are reminded of their importance to the trial.

3. **Parent-Centric Support**

Multiple data collection methods, including use of telephone or in person interviews, champion or researcher support to complete questionnaire if needed, and use of a translator when required, will be provided for participants encountering challenges completing online questionnaires, or facing technical issues. This will be offered at a time and place convenient for the participant to ensure ease of participation.

4. **Clear Points of Contact**

We will provide participants with clear contact information, either via email or phone, for any questions or concerns they may have throughout the study. This helps maintain open communication and fosters a supportive relationship.

5. **Incentives for Engagement**

A £25 shopping voucher will be provided as an incentive for the completion of six-month follow-up questionnaires and £25 for partaking in the in-depth interview. This offers participants additional motivation to stay engaged in the study.

6. **Monitoring Withdrawal and Dropout Reasons**

We will carefully track and record reasons for non-participation, whether participants decline or withdraw. By monitoring these reasons, we will be able to adapt study processes and make improvements, such as proactively reaching out to participants who may be at risk of dropout to address any concerns they may have early on.

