4.3 Control Arm

Parents randomised into the control arm will receive signposting to LBTH and voluntary sector welfare benefits advice service, national websites and helplines.

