4.6 Eligibility Criteria for Individuals Performing the Interventions

The intervention will be delivered by experienced Welfare and Benefits Advisors within three months of randomisation. The UCL Researcher will arrange a WBA appointment at the participant's local CFC (where possible this will be in conjunction with the participant's 6-8 week postnatal check-up). Advice (including welfare benefits, employment, housing, debt) will be provided by LBTH's WBA and will proceed as per service standard. For straightforward cases this is a one off appointment; for others with multiple needs it may include subsequent appointments or referral to a more specialist advice service. As per service standard the advisor will work with the client until optimum financial change has been achieved. A translator will be available during advice sessions when necessary.

5 Assessments & Follow-Up

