5.2 Participant Timeline

Table 2: Schedule of Assessments

Visit Number	Screening	Baseline	Control Group	Intervention group	6-month follow up	Additional follow-up (subsample of participants)
Day/week	Day 0	2 weeks	1-3 months	1-3 months	6 months	6 months
Protocol visit window						
¹ Eligibility screen	X					
¹ Verbal Informed consent	X					
² Written informed e-consent		X				
² Eligibility confirmation	X	X				
Demographics data	X					
² Randomisation / Group allocation		X				
SAE review		X	X	X	X	
Interventions:						
³ Post card detailing LBTH services			X			

⁴ WBA appointment				X		
⁵ Questionnaires:						
EQ-5D-5L		X			X	
GAD-7		X			X	
PHQ-8		X			X	
SWEMWBS		X			X	
Subjective financial situation		X			X	
Self-reported household income		X			X	
⁶ Qualitative Interview						X

¹Initial eligibility screening will be performed by a health visitor and they will obtain verbal consent from interested participants for their contact details to be passed on to the UCL research team who can explain the study.

²Written informed e-consent, eligibility re-confirmation and randomisation will be performed by a UCL Researcher.

³Post card detailing LBTH services (information on where to access welfare benefits advice) to control group only.

⁴WBA appointment to be arranged for intervention group only (where possible to coincide with 6-8 week health check of newborn infant).

⁵Questionnaires will be completed at Baseline and 6-month follow-up. At each time point participants will be chased every 2 weeks for 2 months if the questionnaires have not been completed.

⁶A subsample of 45 participants from both groups will be purposively selected at random to complete an in-depth interview at 6 months.

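### Section 8.2.6 sends the control arm's signposting card after follow-up data are obtained, while Table 2 has the same card at 1-3 months; the protocol must state one timing

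*Protocol*

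**What the plan says.** Section 8.2.6 (Blinding) describes a card, emailed or mailed to controls, that lists the borough's existing advice services. It is to be sent "after their follow up data is obtained and when sending on their thank you voucher". Section 3.3.3 explains the voucher: a £25 "shopping voucher will be provided as an incentive for the completion of six-month follow-up questionnaires".

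Table 2 in section 5.2 lists the card among the interventions. Its mark stands in the control column, headed 1-3 months, and the six-month column has none. Footnote 3 confines the card to the control group.

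Four other sections mention the signposting without dating it:

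- Section 1.1.1: "The second group will receive standard care and be given information on where they can access welfare benefits advice".
- Section 1.3: "Participants who are randomised to the control group will be emailed or posted a card to their address". The card's description is nearly the same as in section 8.2.6 but has no delay clause, and it comes before the paragraph on follow-up questionnaires.
- Section 4.3: "Parents randomised into the control arm will receive signposting to LBTH and voluntary sector welfare benefits advice service, national websites and helplines".
- Section 8.2.2 describes the control group as standard of care with information on where to find advice.

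**The concern.** The card is what the trial delivers to its comparator arm, and the protocol gives two incompatible times for it. One falls before the primary outcome and the other after it.

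If staff follow section 8.2.6, no control has received the trial's signposting when the six-month PHQ-8 is completed. The trial then compares co-located advice with usual services and no trial signposting. If staff follow Table 2, it compares co-located advice with usual services plus signposting, which is how sections 1.1.1, 1.3, 4.3 and 8.2.2 read. If different staff follow different sections, the control condition is mixed. A reader of the results could not tell from the protocol which comparison was made.

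**Working it through.** **Is it the same card?** Yes. Sections 1.3 and 8.2.6 describe its content and recipients in nearly the same terms, and Table 2 with footnote 3 matches both. No section describes a second mailing.

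**Is 1-3 months a delivery time or only an arm label?** A delivery time. The intervention column carries the same heading, and section 4.6 says "The intervention will be delivered by experienced Welfare and Benefits Advisors within three months of randomisation". Even on a loose reading, the column precedes the six-month visit.

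**Does the voucher come after the primary outcome?** Yes. It is given for completing the six-month questionnaires, and the PHQ-8 is one of them (Table 2).

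**Does the amendment log explain the difference?** No. The version 2.0 entry in section 20 lists safety netting, an easy-read information sheet, retention of contact details and administrative changes.

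**Time with the card before the PHQ-8.** Inputs: card at 1 to 3 months (Table 2); follow-up due at 6 months (Table 2); and footnote 5, "At each time point participants will be chased every 2 weeks for 2 months if the questionnaires have not been completed", so completion at 6 to 6 + 2 = 8 months. Assumption: all Table 2 month headings share one clock.

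| Timing followed | Shortest | Longest |
|---|---|---|
| Table 2 | 6 − 3 = 3 months | 8 − 1 = 7 months |
| Section 8.2.6 | 0 | 0 |

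The clock matters little. Table 2 puts screening at day 0 and randomisation at 2 weeks, about half a month. If the 1-3 months run from randomisation and the 6 months from screening, the range is 6 − 3.5 = 2.5 to 8 − 1.5 = 6.5 months. It stays well above zero.

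**Does the sample size depend on this?** The plan's figure reproduces from section 8.1 (difference 1.5, SD 7.25, correlation 0.25, two-sided 5%, 90% power, 20% dropout):

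- Variance after baseline adjustment: 7.25² × (1 − 0.25²) = 49.28.
- Per arm: 2 × (1.960 + 1.282)² × 49.28 / 1.5² ≈ 460.2, rounded up to 461, so 922 in total.
- With dropout: 922 / 0.8 = 1152.5, rounded up to 1153.

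The card's timing is not an input, so 1153 stands under either timing.

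**A side effect of the literal reading.** If the card is sent only once follow-up data are in, controls who never complete follow-up may never get it. With about 1153 / 2 ≈ 576 controls and dropout assumed equal between arms, that is about 0.20 × 576 ≈ 115 people at the planned 20%, or about 58 at the anticipated 10%.

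**The case against.** The best case on the other side is that this is a drafting slip about a leaflet of public information. Several points in it are fair.

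- The trial summary defines Arm B simply as the standard services available in the borough and mentions no card. That fits late sending. The economic comparison in section 9 likewise does not depend on the card. Only Table 2 conflicts with section 8.2.6 on an actual date.
- Controls may use existing services whichever timing applies (section 4.2), and the card reproduces website content (section 8.2.6).
- The 3 to 7 months rest on a one-clock assumption and a two-month chasing window. Section 1.3 allows participation of up to 9 months, and Table 2's visit-window row shows no values.
- Figure 1, the trial diagram, was not available and may show which timing was meant.

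These points limit the consequence and the precision of the month range. They do not remove the contradiction. The broader Arm B wording does not make Table 2 and section 8.2.6 agree. A figure could show which text is the slip, but could not make both true. Nor is this a matter to leave to the statistical analysis plan: when the comparator is delivered belongs in the protocol, and the protocol states it twice, differently.

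**Conclusion.** The concern holds. Section 8.2.6 and Table 2 contradict each other in current text, and this should be fixed. Section 8.2.6 is the likelier error. Sections 1.1.1, 1.3, 4.3 and 8.2.2 treat signposting as part of what controls receive. Section 8.2.6 also gives the alternative advice the purpose of keeping allocation concealed, which a card sent after outcome collection cannot serve during the trial.

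The difference is roughly 3 to 7 months of having the card before the PHQ-8 against none, on the assumptions stated. What is at stake is the definition of the comparator. No effect on PHQ-8 can be estimated from the protocol, and sample size, power and the treatment-policy analysis are unaffected. The conclusion assumes a single mailing, since no other is described, and was reached without sight of Figure 1.

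**What to change.** State one timing throughout.

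- **Preferred:** delete the delay clause from section 8.2.6 and send the card after randomisation, within Table 2's window. Repeat that window in sections 1.3, 4.3 and 8.2.6 so that the date no longer rests on a column heading alone.
- **If delay is intended:** move the mark in Table 2, amend sections 1.1.1, 1.3, 4.3 and 8.2.2, and describe the comparator as usual services without trial signposting before the outcome. Say also whether controls lost to follow-up are sent the card.
- **In either case:** check Figure 1 against the chosen timing.

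A minor correction can go in at the same time. Remove the sentence in section 8.2.6 that credits allocation concealment to the alternative advice; concealment rests on the online randomisation service (section 8.2.1). This has no operational effect.

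The cost is a wording amendment with no change to sample size or analysis. If it is classed as substantial, it needs REC and HRA approval (section 13.2.2).
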